Clinical Trials Cover Page

Treatment Phenotypes for Adolescents with Asthma

Document date 09/22/2023

NCT04228107

COMIRB Protocol

COLORADO MULTIPLE INSTITUTIONAL REVIEW BOARD
[name] [contact] [contact]

Protocol #:19-1861

Project Title: Treatment Phenotypes For Adolescents With Asthma

Principal Investigator: [name] [name]

Version Date:

22-SEP-2023

I. Hypotheses and Specific Aims:

The goal of this proposal is to better characterize medication use patterns among children with asthma and to develop provider and adolescent-focused interventions to respond to poor adherence and poor control. Asthma is the most common chronic disease in children, with a huge impact on healthcare outcomes and expenditures in the US¹. Inhaled controller medications are the cornerstone of asthma therapy and adherence to these medications is critical to effective asthma management. However, commonly used techniques to measure adherence to daily medications are insufficiently accurate²⁻⁶. Reliance on patient reported measures of adherence tends to overestimate true adherence when compared to more objective measurements⁶⁻⁹. Previous evaluations of adherence using electronic monitoring devices have shown lower adherence rates to be correlated with higher levels of healthcare utilization¹⁰, and worsened levels of asthma control^{11,12}. One study found that nearly 1/4 of asthma exacerbations are attributable to inhaled corticosteroid non-adherence¹³. Some estimates indicate that even achieving high adherence for 40% of children with asthma would result in cost savings of \$8.2 million/year¹⁴. Additionally, biologic medications are now available for the treatment of refractory asthma in children, however the high cost of these medications and potential for side effects makes the objective distinction of non-adherence from treatment refractory asthma of paramount importance¹⁵. Medication monitoring technology allows for more accurate measures of medication adherence. Technology for monitoring adherence is expected to be widely available to providers within the next 5-10 years, and providers will need to know how to use patient adherence data to improve their patient outcomes.

Therefore, what is needed is better understanding of medication use patterns and methods of intervening to increase adherence that are feasible to implement in the clinical setting.

Specific Aim 1) To better characterize adherence trajectory phenotypes, and to combine adherence with rescue medication use patterns to create defined asthma treatment phenotypes.

Hypothesis: we will be able to obtain distinct treatment phenotypes utilizing medication monitoring sensors.

Specific Aim 2) Use qualitative methods among adolescents and providers to evaluate reasons for adherence/nonadherence and motivating factors for adherence, feelings about device monitoring and suggested strategies for

intervention among each of the highest risk treatment phenotypes using a self-determination theory framework.

Hypothesis: Qualitative methodology will yield a number of intervention strategies that can be subjected to expert opinion

II. Background and Significance:

- a. **Asthma morbidity is a significant public health problem**, with 7-9 percent of children in the US having a diagnosis of asthma in 2016, and 54% of those children having an asthma exacerbation within that year¹⁶. Asthma exacerbations/hospitalizations remain a significant source of healthcare expenditure¹, with an average inpatient hospitalization in children costing \$3600¹⁷, and an overall cost to the United States of \$81.9 billion per year¹. Asthma reduces productivity, resulting in approximately 14.41 million lost work days and 3.68 million lost school days per year.¹⁸ Across the lifespan, a history of a previous exacerbation is a significant risk factor for a future exacerbation,^{19,20} and has been found to be more predictive of an exacerbation than other variables including race/ethnicity and insurance status¹⁹.
- b. **Inhaled corticosteroids have been shown to significantly improve asthma control**. The use of inhaled corticosteroids (ICS) in asthmatic children and adults has been shown to significantly decrease the rate of asthma-related hospitalization²¹ and asthma related death²². Inhaled corticosteroids have been shown in clinical trials to reduce asthma exacerbations and improve daily asthma control²³⁻²⁵. Recurrent exacerbations are also known to decrease lung function over time²⁶, so improving adherence to decrease exacerbations could have very important long-term implications for asthmatic children.
- c. **Adherence has been correlated with improved asthma outcomes**. Previous evaluations of adherence using electronic monitoring devices have shown lower adherence rates to be correlated with higher levels of healthcare utilization¹⁰, and worsened levels of asthma control^{11,12}. One study found that nearly ¼ of asthma exacerbations are attributable to ICS non-adherence¹³. Some estimates indicate that even achieving high adherence for 40% of children with asthma would result in cost savings of \$8.2 million per year¹⁴. For all diseases, non-adherence to medications is estimated to cost \$100 billion every year in avoidable hospitalizations²⁷.
- d. **Adherence to asthma medications is poor²⁸**, and even with monitoring has been shown to worsen over time²⁹. The large Childhood Asthma Management Program study found that 75% of children studied had adherence levels of less than 80% when measured objectively⁴. In fact, one review of previous attempts to measure adherence to asthma medications utilizing electronic monitoring devices showed adherence rates between 28-73%, with only one study showing an adherence rate above 90%³⁰.

- e. **There is a group of children who are highly adherent to medications but remain poorly controlled** and require escalation to biologic therapy. These therapies are expensive³¹, with one model suggesting that omalizumab may cost as much as \$117,000 per quality adjusted life year¹⁵, so rapid and accurate identification of the appropriate children for this therapy is of high importance. The ability to accurately monitor adherence would permit identification of children whose poor control is related to poor adherence, potentially sparing them these extremely expensive therapies. However, there is a gap between the medications we know will work to control childhood asthma, and the behavior changes that are needed to encourage medication use.
- f. **Use of theory-based approaches to behavior change** is widely recognized as key to developing interventions with demonstrated effectiveness and relevance to real-world practice ³². Self-determination theory (SDT) is a theory of human development and motivation that has been broadly applied to health behavior change. According to SDT, human behavior is regulated along a continuum of motivation ranging from more autonomous (self-determined) to more controlled; greater environmental support for an individual's need for autonomy, competence, and belonging lead to more autonomous forms of motivation (e.g., intrinsic, integrated and identified motivation). Research consistently shows that interventions that support such needs are especially effective for enhancing the motivation and behavior of children and adolescents, including in the health domain ³². Through application of principles and evidence-based behavior change strategies from the SDT literature, in addition to medication use monitoring, there is untapped potential for improving both initial and long-term maintenance of adherence to asthma medications.
- g. **Potential Impact of the proposed study:** This study has the potential to significantly benefit children with asthma by developing the best strategies to sustain high levels of monitored adherence and identify those medication *treatment phenotypes* most in need of clinical intervention. Previous studies, including my previous work on adherence, have shown that adherence levels decline over time, even with monitoring and reminders. A better understanding of why patients follow the specific adherence trajectories that they do is key for sustained success of adherence improvement programs. Understanding adherence patterns could lead to more personalized approaches to asthma medication use, including tailored interventions addressing mechanisms that lead to poor asthma control. The issues studied here could potentially be extrapolated to many other chronic health conditions in children where adherence is also problematic.
- h. **Innovation 1-Methodology: Utilizing group based trajectory modeling to place patients into adherence trajectory groupings.** Group based trajectory modeling has been utilized in evaluations of medication adherence in a number of other disease states including psoriasis³³, cystic fibrosis³⁴, epilepsy³⁵, glaucoma³⁶, and heart disease³⁷ (among others). These evaluations have shown similar adherence trajectory patterns to those seen in our pilot study, with small variations based on the number of

trajectories chosen for the models. We will extend our previous work to evaluate adherence trajectories in asthmatic children, and couple these with rescue medication use measures in order to implement treatment phenotype specific interventions, which has not previously been attempted in asthmatic children.

- i. **Innovation 2-Extend the knowledge base about adherence by using mixed methods pairing qualitative data collection with objective measures of adherence.** Previously identified barriers to asthma medication adherence include lack of routine, forgetfulness and competing demands on time^{38,39}. However, participants in these studies did not have objective measures of adherence to correlate with specific barriers and facilitators. The proposed study will allow for the delineation of barriers and facilitators that are particular to groups with high, low or decreasing adherence, which has not been assessed in children with asthma.
- j. **Innovation 3-Programmatic development that is tailored to each individual patient.** Individualized management programs have been shown to attenuate drops in medication adherence in adult asthma patients using sensor monitoring⁴⁰ and in pediatric patients using medication fills⁴¹. However, such programs have not yet been attempted in children using adherence monitoring.
- k. **Innovation 4-Ability to accurately identify patients who are highly adherent and poorly controlled, and therefore, good candidates for expensive biologic therapies.** New, but expensive therapies such as the monoclonal antibodies omalizumab and mepolizumab are viable options for patients who have poor control but good adherence to traditional therapies. The type of monitoring technology we propose to study could allow for quicker and more accurate characterization of this patient type before they endure exacerbations potentially leading to hospitalizations and irreversible loss of lung function.

III. Preliminary Studies/Progress Report:

Pilot program to evaluate the usability and feasibility of the Propeller Health adherence monitoring device-through this work I gained skills working with this technology and population of asthmatic children

- a. 25 children with high risk asthma (at least one hospitalization or 2 ED visits within the last year), monitored for 3 months.
- b. Devices were well accepted by parents, children and providers, with little to no concerns from families about ease of use.
- c. Average adherence rate of about 56% over the 3 month time period studied, however average adherence started at 78% and dropped to 36% by the end of the study⁴².

Breathing Counts Program-through this work I gained skills of working with this technology and this population, as well as beginning to address adherence barriers

[figure not shown]

Figure 1 Adherence trajectories after 3 months of monitoring in asthmatic children (n=65)

- d. Adherence measured plus an asthma health educator who contacted families at regular intervals to discuss adherence and address barriers.
- e. 65 patients monitored for a total of 6 months per patient
- f. Has added significantly to our knowledge, by identifying likely barriers to adherence, identifying adherence trajectories after 3 months of monitoring (Fig 1), confirming that 61% of patients fell into a suboptimal adherence category, and dealing with technical support issues that might arise with the devices.

Propeller Health database evaluation-through this work I have continued to evaluate the adherence trajectories over time in a diverse population of asthmatics.

- g. Initial data presented at the 2018 American Thoracic Society meeting showing stability of initial adherence trajectories over 20 weeks of monitoring in 1,234 patients. Manuscript under review
- Financial Incentives for medication use
- h. Evaluating the use of financial incentives for asthma medication use in asthma
- i. 43/50 patients enrolled to date.

In the current proposal, I have decided to focus the evaluation on adolescents with asthma as they are a group at high risk for non-adherence, and they are often responsible for their own medication use, as opposed to younger children who depend on their parents for medication administration. I have enrolled a significant number of adolescent asthmatics in the previous two studies discussed, and I have experience in working with this age group. Additionally, I have extensive experience using the adherence monitoring devices and I am well equipped to address any technical issues that may arise.

IV. Research Methods

Specific Aim 1) To better characterize adherence trajectory phenotypes, and to combine adherence with short acting beta agonist (SABA) use patterns to create defined asthma *treatment phenotypes*.

Hypothesis: We will be able to identify distinct *treatment phenotypes* during the 12 months of monitoring.

Study Design: Longitudinal, prospective, cohort study of the medication adherence patterns of children with high risk asthma during which time they will receive adherence monitoring and notifications.

Study Setting Patients who have been seen within the last 2 years by the Pulmonary, Allergy and/or Child Health/Adolescent Medicine clinics at Children's Hospital Colorado (CHCO) Main Campus, and network-of-care sites including: Briargate, North Campus, South Campus, Parker, and CHCO in Colorado Springs. These clinics treat a variety of patients; however, a significant proportion of these patients are asthma sufferers, and the pulmonary clinic alone sees over 3000 asthma visits per year. Patients who are currently, or have been, admitted to CHCO for an asthma exacerbation may also be approached.

Study Population The study population will include children with a diagnosis of asthma, either in their "Problem List" or "Visit Diagnosis", aged 12-16 years old at the time of consent, on an inhaled controller and rescue medication that can fit the Propeller Health devices. For patients who follow the new NIH-approved SMART (single maintenance and reliever therapy) approach, their inhaled controller medication and rescue medication will

be the same. Exclusion criteria will include co-morbidities such as other significant chronic lung disease (cystic fibrosis, chronic respiratory failure, tracheostomy status, interstitial lung disease, restrictive lung disease, bronchopulmonary dysplasia, pulmonary hypertension, bronchiectasis, chronic lung disease of prematurity) on their problem list, significant developmental delay on their problem list, taking more than 3 asthma related medications (other than their quick relief medication), or primary language other than English, Spanish, Catalan, Dutch, French, German or Italian (the languages currently supported for the monitoring application), or if patients do not have a smartphone that can download the Propeller Health app. We plan to enroll 100 patients using a rolling enrollment plan over a period of 6-12 months.

Outcome Measures The primary outcome for this Specific Aim will be the medication treatment phenotype as determined by Group Based Trajectory Modeling (GBTM)⁴³. We will analyze trajectories at the completion of 2, 4, 6, 8 and 12 months of monitoring for all patients in order to determine how rapidly the treatment phenotypes are established, as well as how stable they are over time.

Study Procedures We will screen for eligible participants by reviewing clinic schedules for the Pulmonary, Allergy, Child Health/Adolescent Medicine clinics, and recent admissions on a regular basis. Additionally, we may utilize EMR tools to identify all patients seen in these clinics in the past 2 years to reach out to families directly. Due to current practice changes during the COVID-19 pandemic, patients and parents will be consented either in clinic, while admitted to CHCO, or by Telehealth after a clinic visit by a member of the study team. Remote consent will be done via Vidyo on the MyChart platform, and participant ability to login to the MyChart application will be considered verification of identity for the purposes of consenting. We will use REDCap to house electronic consent documentation. If the consent occurs in person, a copy of the signed consent form will be given to the family. If the consent occurs via Telehealth, the REDCap consent responses will be emailed or mailed via USPS standard mail to the participant after the consent visit is complete. After consent is obtained and upon receipt of the Propeller Health device either in the clinic, inpatient room, or in their home, patients will be enrolled in medication use monitoring with mobile sensor technology. Participants will be given sensors to attach to their controller and rescue medications. For participants who have one medication for both their controller and rescue inhaler, they will only receive one sensor. If the consent happens in clinic or while admitted, the patients will be enrolled in the Propeller Health system at the same time. If consent occurs remotely, a second telehealth visit may be scheduled after the consent has been signed if the devices have not been received by the participant. If the patient has already received the devices, they will be enrolled in the Propeller health system immediately after consent. The sensors will sync via Bluetooth to an application on the participant's or parent's phone (or both based on participant preference) to provide feedback and reminders regarding medication adherence (push notifications will be sent if medications have not been used 15 min after the time specified by the participant on enrollment as the time they normally take their medications). Patients will be given the option to share their data with their healthcare provider, however providers will not have direct access to this data. Data will be collected regarding the exact time of inhaler actuation indicating a dose of medication being delivered. Additionally, at study entry, we will collect information regarding basic baseline demographic and clinical information (including age, medications prescribed, allergic history, lung function and secondhand smoke exposure). Participants will be given the option to receive text message reminders from the study team regarding sensor inactivity. Participants will be asked to sync their sensors to their phone application prior to disposing of the Bluetooth devices in order to remove data from the device memory. If

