We will determine levels of asthma control based on NHLBI EPR-3 guidelines defining asthma impairment⁴⁴. Asthma control will be defined on a weekly basis, with albuterol use <2 times per week labeled as good control, albuterol use daily labeled as poor control, and albuterol use multiple times per day labeled as very poor control. When defining a *treatment phenotype*, the poor control and very poor control groups will be combined as 'poor control'. All albuterol actuations occurring within 5 minutes will be considered a single use event. Albuterol actuations occurring outside this 5-minute window from the first actuation will be considered a separate albuterol use event. When defining a *treatment phenotype* at the end of the monitoring period, we will consider a patient to have 'poor control' if they demonstrate poor or very poor control based on the parameters above for >50% of the measured weeks of monitoring, or if they have an exacerbation requiring oral steroids during the monitoring period.

Potential Problems and Alternative Approaches

Inability to confirm adherence trajectories. The null hypothesis is that we will not be able to identify defined adherence trajectories and therefore *treatment phenotypes*. Traditional power analysis techniques do not currently exist for the group based trajectory modeling approach and this is an active field of current methodologic research. While we are reasonably confident that we will be able to successfully determine adherence trajectories based on our previous research with smaller groups of patients as well as the work in other disease states, there is a small chance that we will not be able to confirm the group based adherence trajectories. However, we will be able to evaluate medication use patterns per the other methods described above (average adherence over time). Additionally, if adolescents shift their adherence trajectories over time, we will do an in-

depth analysis to evaluate possible reasons for the change (including provider interventions and significant exacerbations).

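### Participants using one inhaler as both controller and rescue (SMART) have one sensor, and the plan gives no rule that yields a valid control label or adherence value for them

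*Combined protocol and SAP*

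**What the plan says.** All references are to the combined protocol and SAP.

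- **Aim.** Section I sets out "to combine adherence with rescue medication use patterns to create defined asthma treatment phenotypes". Section IV (Outcome Measures) makes the treatment phenotype the primary outcome.
- **Eligibility.** Section IV (Study Population) reads "For patients who follow the new NIH-approved SMART (single maintenance and reliever therapy) approach, their inhaled controller medication and rescue medication will", and the sentence ends by saying that the two are the same. On sample size: "We plan to enroll 100 patients". The number or share on SMART is not given.
- **Sensors.** Section IV (Study Procedures): "For participants who have one medication for both their controller and rescue inhaler, they will only receive one sensor". The data described are actuation times. The participant's usual dosing time is mentioned only as the trigger for reminders.
- **Control.** Section IV (Asthma Control) defines each week "with albuterol use <2 times per week labeled as good control" and "albuterol use daily labeled as poor control", with several uses per day as very poor. The event rule is likewise specific to the drug: "All albuterol actuations occurring within 5 minutes will be considered a single use event". At the end of monitoring a patient has poor control if weeks were poor or very poor "for >50% of the measured weeks of monitoring", or after an exacerbation treated with oral steroids.
- **Adherence.** Section IV (Adherence trajectory modeling) models average weekly adherence and, as an alternative, classes 12-month mean adherence as high (above 80%), moderate (30-80%) or poor (below 30%). It does not say what to do with rescue puffs from a shared inhaler.

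**The concern.** SMART was written into eligibility and sensor allocation but not into the analysis. For most participants, one sensor informs adherence and another informs control. For a SMART participant, a single stream of time stamps has to serve both, and nothing says which actuations belong to which component.

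Two things are at stake. First, Innovation 4 in the Background wants to find patients who adhere well and are still poorly controlled. Whether a symptomatic SMART user can reach that group depends on a choice that the plan leaves to the analyst. Second, the trajectory model places each patient using data from the whole group, so invalid adherence curves from these participants also enter the fit for everyone else.

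**Working it through.** The plan calculates no figure on this point, so there is none to reproduce. The check applies the written rules to a single-sensor participant under each available reading.

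**Inputs from the protocol:** one sensor; good control below 2 albuterol events a week; poor control at daily use; very poor control at several uses a day; the >50% rule; the 30% and 80% adherence cut-offs; 100 patients.

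**Assumptions, for illustration only:** 28 scheduled puffs a week (two 2-puff sessions a day); one 2-puff rescue event a day (14 puffs a week); the puffs of one session fall within 5 minutes.

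**Readings for control**

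1. *Absent albuterol is zero.* Events per week = 0, and 0 < 2, so every week is good. Poor weeks are 0 of 52, so the >50% route can never be met, at any true rescue frequency. Only an oral-steroid exacerbation gives poor control.
2. *Absent albuterol is unmeasured.* There are no measured weeks, so the >50% rule has no denominator. Control is undefined unless an oral-steroid exacerbation occurs.
3. *Every actuation is rescue.* Events per week = 7 × sessions per day × adherence + rescue events. For a fully adherent, symptom-free user, one session a day gives 7 × 1 × 1.00 = 7 (daily, so poor) and two sessions give 7 × 2 × 1.00 = 14 (several a day, so very poor). At two sessions and 80% adherence, 7 × 2 × 0.80 = 11.2, which averages more than one a day.

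**Reading for adherence**

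4. *Every actuation is adherence.* Recorded adherence = (true adherence × scheduled puffs + rescue puffs) / scheduled puffs. At a true 40%: (0.40 × 28 + 14) / 28 = 25.2 / 28 = 90%. This moves the patient from moderate to high on the mean-adherence cut-offs. The inflation is 14/28 = 50 points; it would be 14/56 = 25 points at 56 scheduled puffs a week and 14/14 = 100 points at 14, before any cap.

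**What a cap achieves.** Credit at most one session per dosing period, and assume the daily rescue event falls in one of two half-day periods independently of whether that dose was taken. Recorded adherence is 0.40 + (1 − 0.40)/2 = 70%, against 90% uncapped and 40% true. The cap helps but does not remove the bias.

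**What time-window attribution achieves.** Further assumptions: doses at 07:00 and 20:00 with an SD of 30 minutes, and rescue uniform over 07:00-22:00.

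- Windows of ±2 h cover 2 + 4 = 6 of 15 hours (40%) of rescue times. A true 40% is recorded as (2 × 0.40 + 0.40 × 0.60)/2 = 52%. With ±1 h the result is 44%.
- If daily means all seven days, the share of weeks scored poor at ±2 h is [1 − 0.40 × (1 − a)]^7, where a is true adherence. At a = 0.90 this is 0.96^7 = 75%, so the label is recovered. At a = 0.40 it is 0.76^7 = 15%, so it is not.
- Narrow windows create false rescue events. With an SD of 60 minutes and ±1 h, 68.3% of doses fall inside. A symptom-free user at 90% is recorded as 0.90 × 0.683 = 61%, with 14 × 0.90 × 0.317 = 4.0 false events a week.

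**Number affected.** 100 × 5%, 10% and 20% = 5, 10 and 20 participants, at assumed shares.

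**The case against.** A reader might infer that, followed literally, the plan scores every week of every SMART participant as good, so that the error always hides poor control. The documents do not support this. The rule refers to measured weeks, and a participant without an albuterol sensor has albuterol unmeasured, not measured at zero. Nor is the direction settled. Because the protocol says that controller and rescue are the same medication for these patients, an analyst could score that inhaler as rescue, which pushes adherent users towards poor control. Well-controlled SMART users keep the right label under the zero reading but not under that one.

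It can also be said that Section IV restates Aim 1 in terms of short-acting beta agonist use, which agrees with the albuterol rule. That is so, and the rule is coherent for two-inhaler participants. It does not help those whose rescue inhaler is not a separate device.

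The Asthma Control Test is named in the paragraph on diverse populations, but to address cut points, and it is not part of the weekly or phenotype rule. The oral-steroid route stays open to everyone, so poor control is not unreachable.

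Finally, the size is unknown and every puff count and timing above is assumed. That stands, and it limits what can be said about impact. It does not supply the missing rule.

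**Conclusion.** The gap is real and concerns the definition of the primary outcome: for single-sensor participants the plan yields neither a valid weekly control label nor a valid adherence value. This rests on the text alone. The direction of the resulting error is undetermined, because the readings give opposite labels to the same patient. The size is also undetermined, because the SMART share is not stated; 5 to 20 of 100 is a range under assumed shares. The 40%-to-90% example shows what crediting all actuations can do and is not an estimate for this cohort. It should be fixed before analysis.

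The label for weeks with two or more uses but less than daily use, and the meaning of daily, are also left open in the Asthma Control section. They affect all participants and should be raised as a separate point.

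**What to change.** Before analysis, add to the plan:

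1. **Control.** Do not apply the albuterol weekly rule to single-sensor participants. Record their weekly control as not assessable (missing), never as good, and keep the oral-steroid exacerbation route to poor control.
2. **Adherence.** Do not credit all their actuations. Cap credited doses at the prescribed scheduled number per dosing period, and define that period. Report the trajectories and phenotypes with and without single-sensor participants.
3. **Sensitivity analysis.** Where the dosing time and current regimen are available, attribute actuations to scheduled or rescue use from the time stamps, with several window widths. Cross-check against the Asthma Control Test where it was collected.

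**Cost.** Plan wording and recoding of time stamps already collected; no change to treatment or visits. The cap needs the prescribed regimen, which is described as collected at study entry only, so later changes to or from a single inhaler may need updating. Step 3 needs the dosing time, which is described only as a reminder setting and may have to be exported.

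**Downside.** Some participants will have no sensor-based control label. Capped adherence can still be inflated by rescue puffs in unfilled dosing periods (70% against a true 40% in the half-day illustration), so the analysis without these participants is needed alongside the cap. Attribution is secondary because it misses low adherers with daily rescue use and can turn late doses into false rescue events.
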